4.1 Inclusion Criteria

1. Written informed consent obtained prior to any study-related procedure being performed;
2. Patients at least 18 years of age or older at the time of consent;
3. Patient with TDT or NTDT syndromes and iron overload currently receiving iron chelation therapy with Jadenu or Exjade and demonstrating inadequate response assessed with serum ferritin and LIC;
4. Stable dosing with Jadenu or Exjade for >3 months prior to screening and receiving the maximal dose (Jadenu: 28 mg/kg or Exjade: 40 mg/kg);
5. Serum ferritin levels that are persistently >800 mcg/L determined by 2 separate assessments during screening over the previous 2-4 weeks prior to study treatment and not showing a decreasing trend over these weeks;
6. An LIC of >5 mg Fe/g dw measured by MRI in the 52 weeks prior to study entry;
7. Compliant with chelation therapy in the 3 months prior to enrollment as assessed by the Investigator:
 - a. Satisfaction with Iron Chelation Therapy (SICT) Quality of Life (QoL) composite score $\geq 60\%$, or determined by investigator that at least 75% of medication prescribed on a regular basis was taken (Investigator enquiry into patient prescription refill records, preferably 3 months if available); and
 - b. Willing to comply with chelation therapy for the duration of the study;
8. Agree not to use other anti-chelating agents concurrently;
9. Eastern Cooperative Oncology Group Performance Status (ECOG PS) of 0-1;
10. Women of childbearing potential (WOCBP) must use an adequate method of birth control (double barrier, e.g. hormonal control and barrier contraception) at least 28

days prior to the first administration of the study drug, during the study and for at least 30 days after the last dose of the study drug. (Section 7.5 for details);

11. Male patients whose partners are WOCBP must use an adequate method of birth control (double barrier control) at least 28 days prior to the first administration of the study drug, during the study and for at least 30 days after the last dose of the study drug; and
12. Patient is willing and able to comply with all protocol required visits and assessments.

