4.2 Exclusion Criteria

1. Patients with life expectancy less than 6 months;
2. Females of childbearing potential not on an adequate method of birth control, or who are pregnant or lactating;
3. History of non-compliance with chelation therapy (determined by the investigator, persistently taking less than 75% of prescribed dose in the 3 months prior to enrollment, or as determined by the Investigator based on medical history, SICT QoL overall score <60% or score in any SICT domain <50%);
4. Screening blood counts of the following:
 - a. Absolute neutrophil count < 1500/ μ L
 - b. Platelets < 100,000/ μ L
 - c. Hemoglobin < 8 g/dL; transfusion support is permitted;
5. Screening chemistry values of the following:
 - a. Alanine aminotransferase (ALT) and aspartate transaminase (AST) > 2.5 \times upper limit of the normal reference range (ULN)
 - b. Total bilirubin > 2 \times ULN
 - c. Creatinine > 1.5 \times ULN
 - d. Urine protein/creatinine ratio (UPCR) >0.5 mg/mg
 - e. Albumin < 2.8 g/dL;
6. History of congestive heart failure New York Heart Association (NYHA) class III or IV or uncontrolled hypertension at screening;

7. History of other malignancy within the previous 3 years, except basal cell or squamous cell carcinoma, or non-muscle invasive bladder cancer;
8. In the opinion of the Investigator, evidence of major inflammatory disease that would affect ferritin levels within 14 days prior to the start of study medication;
9. Major surgery within 30 days prior to the start of study medication;
10. Serious persistent infection within 14 days prior to the start of study medication;
11. Serious concurrent medical condition including central nervous system (CNS) disorders;
12. Requires concomitant treatment with systemic corticosteroids, or any other immunosuppressive agents, or has used such treatment in the past 10 days before study entry (use of prednisone or equivalent <10 mg/day orally or use of inhaled corticosteroids or topical steroids is permitted).
13. Previous history of difficulty swallowing oral medications;
14. Any condition that, in the opinion of the Investigator, would impair the patient's ability to comply with study procedures or study medication; or
15. Concomitant treatment with medications described in [Section 7.4](#) "Prohibited Medications".

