APPENDIX D: SICT QUESTIONNAIRE

The combination of scores for each domain, as well as disease (Thalassemia having the worst adherence), age, missed doses have a high correlation with Non-Compliance.

SICT item Satisfaction domain

All SICT Item responses are averaged along the response scale from 1 to 5 such that a higher satisfaction domain score indicates a high level of satisfaction.

Perceived Effectiveness of ICT (6 items) (lower scores in this domain indicative of non-compliance)

Acceptance of ICT (5 items) (higher scores in this domain indicative of non-compliance)

Burden of ICT (5 items) (higher scores in this domain indicative of non-compliance)

Side Effects of ICT (3 items) (higher scores in this domain indicative of non-compliance)

The SICT used here is modified to exclude questions where there was no significant association, above.

Scoring:

1. A total score for each domain would be calculated using an adjusted mean % score, compared to the total possible score of 100%.
2. Consideration for age is judgmental – adolescents suggested with lower compliance.
3. Higher number of missed doses is suggestive of non-compliance.

DisperSol Technologies, LLC
Protocol Number: DST-0509-201 Subject Initials: _____ Subject #: _____ Date: _____

Eligibility Visit SICT Questionnaire

Instruction:

This questionnaire is intended to assess your Satisfaction with Iron Chelation Therapy (SICT) Quality of Life (QoL). Please rate the following questions on a scale of 1 – 5 as best as you can. Additional details regarding the scale are included within each section. Please only answer each question once.

Group 1: Perception of Health

< Strongly Disagree.....Neutral.....Strongly agree> 1 2 3 4 5		Patient Rating
1.	In the past three months, did you feel your current chelation therapy would help with a longer life?	
2.	In the past three months, did you feel your current chelation therapy would reduce your excess iron?	
3.	In the past three months did you feel your chelation therapy would stop your condition from getting worse?	
4.	In the past three months, did you think your chelation therapy was actually working?	
5.	In the past three months, did you feel that chelation therapy was worthwhile?	

Group 2: Acceptance of Therapy

		Patient Rating
1.	In the past three months, how would you rate the ease for you to take your chelation therapy? <Easy.....Difficult> 1 2 3 4 5	

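### Inclusion 7a and exclusion 3 define compliance in conflicting ways, so a patient with documented intake of at least 75% can be excluded on a satisfaction score alone

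*Protocol*

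**What the plan says.** Protocol section 4.1, inclusion 7, requires compliance over the three months before enrolment, as assessed by the investigator. Item 7a gives two routes. The first is a "Satisfaction with Iron Chelation Therapy (SICT) Quality of Life (QoL) composite score" of at least 60%. The second is joined to it by an alternative: "or determined by investigator that at least 75% of medication prescribed on a regular basis was taken". Refill records are named as the source for the second route, where available.

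Section 4.2, exclusion 3, excludes a history of non-compliance. Its first limb is "persistently taking less than 75% of prescribed dose in the 3 months prior to enrollment". It continues "or as determined by the Investigator based on medical history" and then, after a comma, "SICT QoL overall score <60% or score in any SICT domain <50" (the last figure being a percentage). The synopsis repeats both criteria.

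Inclusion 3 restricts the trial to patients "demonstrating inadequate response assessed with serum ferritin and LIC". Inclusions 4 to 6 add maximal dosing, persistently raised ferritin and raised liver iron.

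Appendix D describes the SICT. One domain is "Perceived Effectiveness of ICT (6 items) (lower scores in this domain indicative of non-compliance". Its items on the form (Group 1) include "In the past three months, did you think your chelation therapy was actually working". Domain scores are an adjusted mean percentage, with the adjustment not defined.

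**The concern.** The two criteria address one construct over one period, but with opposite logic. Under 7a one satisfactory measure is enough. Under exclusion 3 one unsatisfactory measure can be enough to exclude, and the single-domain threshold has no counterpart in 7a. The protocol offers intake as a sufficient alternative to the questionnaire and then appears to withdraw it.

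The conflict matters because of whom the trial wants: patients who take the drug at maximal dose and still respond inadequately. One SICT domain asks whether the patient believes the therapy works, and a low score there counts towards non-compliance. An adherent patient who reports accurately that the drug is failing moves towards exclusion. At stake are the composition of the enrolled population and consistency of screening between sites.

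**Working it through.** **1. Eligibility logic on the literal reading.** Let A = intake at least 75%, S = overall SICT at least 60%, D = every SICT domain at least 50%.

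- 7a is met if A or S.
- Exclusion 3 applies if not A, or not S, or not D.

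| A | S | D | 7a met | Exclusion 3 applies |
|---|---|---|---|---|
| no | no | no | no | yes |
| no | no | yes | no | yes |
| no | yes | no | yes | yes |
| no | yes | yes | yes | yes |
| yes | no | no | yes | yes |
| yes | no | yes | yes | yes |
| yes | yes | no | yes | yes |
| yes | yes | yes | yes | no |

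7a is met in 6 of 8 rows, and exclusion 3 applies in 5 of those 6. Only a patient passing all three tests enters, so the alternative in 7a has no effect. Three of the five conflicts are in patients with adequate intake (the last rows but one). A patient with complete refill records and an overall SICT of 55% is one of them.

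**2. What the effectiveness domain can do by itself.** Group 1 has five items scored 1 to 5. As the adjustment is undefined, two plausible scalings are assumed: (a) mean/5 and (b) (mean − 1)/4.

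- All five items answered 2: (a) 2/5 = 40%; (b) (2 − 1)/4 = 25%. Both are below 50%.
- Answers 3, 2, 2, 1, 3 (sum 11): (a) 11/25 = 44%; (b) (11 − 5)/20 = 30%. Both are below 50%.
- Answers 3, 3, 3, 1, 3 (sum 13): (a) 13/25 = 52%; (b) (13 − 5)/20 = 40%. The result depends on the scaling.

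In the second case, give the other 13 items on the form the best possible score, recoded to 5. The overall score is (11 + 65)/90 = 84% under (a) and (76 − 18)/72 = 81% under (b). The composite passes 60% easily, so the single-domain limb alone excludes the patient.

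**3. Scoring direction in Appendix D.** The appendix says a higher domain score means more satisfaction. It then says higher Acceptance, Burden and Side Effects scores point to non-compliance. On the form, 1 is the favourable end for those three groups, and no reverse-coding is stated. Scored as written, a fully satisfied patient (5 on the five Group 1 items, 1 on the other 13) gets:

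- 1/5 = 20% under (a), or 0% under (b), in each of three domains;
- overall (25 + 13)/90 = 42% under (a), or (38 − 18)/72 = 28% under (b).

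That patient fails both SICT cut-offs. The appendix also counts six effectiveness items where the form has five.

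**4. Number of patients.** No SICT score distribution is given, so the proportion affected cannot be calculated.

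**The case against.** The strongest reply is that exclusion 3 is loosely punctuated. The SICT cut-offs follow the reference to the investigator's determination and can be read as inputs to judgement. That fits inclusion 7, which is also assessed by the investigator, and the schedule notes, which list SICT among additional measures of compliance. On that reading a low score does not exclude automatically. This stands as a reading, but it does not remove the conflict: the same records and score can then lead to enrolment at one site and exclusion at another.

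A second reply is that several adherence checks are reasonable when poor adherence can pass for poor response. That is fair as a design choice. However, 7a as written makes a different choice, and both cannot stand.

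Several stronger inferences are tempting and are not supported:

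- That some sites will apply 7a and others exclusion 3. Section 4 requires all criteria to be met, so no site chooses between them. Variation comes from the ambiguous wording of exclusion 3.
- That any patient who says the drug is not working is excluded. Only one Group 1 item asks this directly. Rating it 1 and the rest 3 gives 52% under mean/5, which passes. Group 1 also asks about longer life and whether therapy is worthwhile.
- That every conflict does harm. A patient with SICT 65% and 60% intake is excluded for low intake, which suits a trial of compliant patients.
- That a fixed share of the 36 is lost. Thirty-six is the cap on randomised patients. Those affected are screen failures, and the cap can still be filled.

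**Conclusion.** The contradiction is real, stands in the current text of both section 4 and the synopsis, and survives either reading of exclusion 3. Literally, the alternative in 7a is void. Loosely, the outcome depends on the site. In both cases a patient with documented intake of at least 75% can be excluded on satisfaction alone, including on a domain that reflects the very inadequate response the trial recruits for.

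The eligibility logic needs no numerical assumption. The domain examples rest on two assumed scalings; the all-2 and the 3, 2, 2, 1, 3 patterns fall below 50% under both. How many patients would be affected is unknown.

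A reader might infer a biased treatment comparison. The documents do not support that: each patient receives both treatments, and selection takes place before randomisation. The consequences are for screening, for consistency between sites, and for the population to which the results apply. It is worth amending, but it does not undermine the crossover comparison.

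**What to change.** Rewrite 7a and exclusion 3, with their synopsis copies, so that one is the exact complement of the other:

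1. Where refill or intake records exist for the three months, documented intake of at least 75% is sufficient for compliance and lower intake is non-compliance.
2. SICT is used only where no such record is available, with the same cut-off in both criteria and a statement of whether it is automatic or advisory.
3. The any-domain limb is removed as an automatic exclusion.
4. Before any SICT cut-off is applied, Appendix D states the direction of each domain, any reverse-coding, the percentage scaling and the correct item count.

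Whether perceived effectiveness belongs in the fallback score can be left to the sponsor. Removing it now would leave only the domains whose direction Appendix D contradicts.

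The cost is a text amendment to two criteria in two places and to the appendix scoring. Refill records are already requested where available, so no new procedure is needed. The downside is that such records may overstate intake in a few patients.

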4.2 Exclusion Criteria

1. Patients with life expectancy less than 6 months;
2. Females of childbearing potential not on an adequate method of birth control, or who are pregnant or lactating;
3. History of non-compliance with chelation therapy (determined by the investigator, persistently taking less than 75% of prescribed dose in the 3 months prior to enrollment, or as determined by the Investigator based on medical history, SICT QoL overall score <60% or score in any SICT domain <50%);
4. Screening blood counts of the following:
 - a. Absolute neutrophil count < 1500/ μ L
 - b. Platelets < 100,000/ μ L
 - c. Hemoglobin < 8 g/dL; transfusion support is permitted;
5. Screening chemistry values of the following:
 - a. Alanine aminotransferase (ALT) and aspartate transaminase (AST) > 2.5 \times upper limit of the normal reference range (ULN)
 - b. Total bilirubin > 2 \times ULN
 - c. Creatinine > 1.5 \times ULN
 - d. Urine protein/creatinine ratio (UPCR) >0.5 mg/mg
 - e. Albumin < 2.8 g/dL;
6. History of congestive heart failure New York Heart Association (NYHA) class III or IV or uncontrolled hypertension at screening;

7. History of other malignancy within the previous 3 years, except basal cell or squamous cell carcinoma, or non-muscle invasive bladder cancer;
8. In the opinion of the Investigator, evidence of major inflammatory disease that would affect ferritin levels within 14 days prior to the start of study medication;
9. Major surgery within 30 days prior to the start of study medication;
10. Serious persistent infection within 14 days prior to the start of study medication;
11. Serious concurrent medical condition including central nervous system (CNS) disorders;
12. Requires concomitant treatment with systemic corticosteroids, or any other immunosuppressive agents, or has used such treatment in the past 10 days before study entry (use of prednisone or equivalent <10 mg/day orally or use of inhaled corticosteroids or topical steroids is permitted).
13. Previous history of difficulty swallowing oral medications;
14. Any condition that, in the opinion of the Investigator, would impair the patient's ability to comply with study procedures or study medication; or
15. Concomitant treatment with medications described in [Section 7.4](#) "Prohibited Medications".

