5.4 Administration of Investigational Product

DST-0509 will be supplied in 360 mg, 180 mg and 90 mg tablets. Jadenu is commercially available as tablets and Exjade as tablets for oral suspension and will be provided by the patient with their ongoing prescription. Dosing will be at equivalent (mg for mg) doses of DST-0509 or Jadenu. If converting from Exjade, the dose will be scaled for each treatment by 28 mg/40 mg (treatment/Exjade).

This is an open-label crossover study. Patients will receive Exjade or Jadenu at their previous stable dose. DST-0509 is taken with food, Jadenu is taken with or without a light meal, and Exjade is recommended to be taken without food. However, either Jadenu or Exjade can be administered according to the patient's previous regimen.

Each subject will be provided with sufficient DST-0509 for the respective treatment period and site staff will ensure prescription for Jaden and Exjade are sufficient for the respective treatment periods. The first dose will be taken at Visit 3 (Day 1) and the final dose will be taken at Visit 10 (Day 63).

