4 CONTRAINDICATIONS

Exjade is contraindicated in patients with:

- Serum creatinine greater than 2 times the age-appropriate upper limit of normal or creatinine clearance less than 40 mL/min [see *Warning and Precautions (5.1)*];
- Poor performance status;
- High-risk myelodysplastic syndromes;
- Advanced malignancies;
- Platelet counts <50 x 10⁹/L;
- Known hypersensitivity to deferasirox or any component of Exjade [see *Warnings and Precautions (5.6)*, *Adverse Reactions (6.2)*].

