2.5 Dose Modifications for Increases in Serum Creatinine

For serum creatinine increases while receiving JADENU [see *Warnings and Precautions (5.1)*] modify the dose as follows:

Transfusional Iron Overload

Adults and Adolescents (ages 16 years and older):

- If the serum creatinine increases by 33% or more above the average baseline measurement, repeat the serum creatinine within 1 week, and if still elevated by 33% or more, reduce the dose by 7 mg per kg.

Pediatric Patients (ages 2 to 15 years):

- Reduce the dose by 7 mg per kg if serum creatinine increases to greater than 33% above the average baseline measurement and greater than the age appropriate ULN.

All Patients (regardless of age):

- Discontinue therapy for serum creatinine greater than 2 times the age-appropriate ULN or for creatinine clearance less than 40 mL/min. [see *Contraindications (4)*]

Non-Transfusion-Dependent Thalassemia Syndromes

Adults and Adolescents (ages 16 years and older):

- If the serum creatinine increases by 33% or more above the average baseline measurement, repeat the serum creatinine within 1 week, and if still elevated by 33% or more, interrupt therapy if the dose is 3.5 mg per kg, or reduce by 50% if the dose is 7 or 14 mg per kg.

Pediatric Patients (ages 10 to 15 years):

- Reduce the dose by 3.5 mg per kg if serum creatinine increases to greater than 33% above the average baseline measurement and greater than the age appropriate ULN.

All Patients (regardless of age):

- Discontinue therapy for serum creatinine greater than 2 times the age-appropriate ULN or for creatinine clearance less than 40 mL/min [see *Contraindications (4)*].

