4 CONTRAINDICATIONS

JADENU is contraindicated in patients with:

- Serum creatinine greater than 2 times the age-appropriate ULN or CrCl less than 40 mL/min [see *Warning and Precautions (5.1)*];
- Poor performance status;
- High-risk myelodysplastic syndromes;
- Advanced malignancies;
- Platelet counts $<50 \times 10^9/L$;
- Known hypersensitivity to deferasirox or any component of JADENU [see *Warnings and Precautions (5.6), Adverse Reactions (6.2)*].

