8.6 Renal Impairment

For patients with renal impairment (ClCr 40 to 60 mL/min), reduce the starting dose by 50% [see *Dosage and Administration* (2.4), *Clinical Pharmacology* (12.3)]. JADENU is contraindicated in patients with a ClCr < 40 mL/min or serum creatinine > 2 times the age-appropriate ULN [see *Contraindications* (4)].

JADENU can cause renal failure. Monitor serum creatinine and calculate ClCr (using Cockcroft-Gault method) during treatment in all patients. Reduce, interrupt or discontinue JADENU dosing based on increases in serum creatinine [see *Dosage and Administration* (2.4, 2.5), *Warnings and Precautions* (5.1)].

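### Exclusion 5c screens renal filtration by serum creatinine alone, so some lighter or older patients with creatinine clearance below 40 mL/min, a contraindication in both appended labels, can be enrolled

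*Protocol*

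**What the plan says.** Exclusion 5 in Section 4.2, repeated in the synopsis, has two renal items. Item 5c excludes on serum creatinine ("c. Creatinine > 1.5" × ULN). Item 5d excludes on a urine protein/creatinine ratio above 0.5 mg/mg, which measures proteinuria rather than filtration. Neither the Visit 1 and Visit 2 procedures (Sections 6.1 and 6.2) nor the laboratory list (Section 7.11.1) mentions creatinine clearance. In the body of the protocol it appears only as background in Section 1.2.

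The labels appended to the same protocol set two alternative limits:

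- Exjade (Appendix A, Section 4): "Serum creatinine greater than 2 times the age-appropriate upper limit of normal or creatinine clearance less than 40 mL/min".
- Jadenu (Appendix B, Section 4): "Serum creatinine greater than 2 times the age-appropriate ULN or CrCl less than 40 mL/min".

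The Jadenu label repeats the threshold as a stopping rule in its Section 2.5 ("Discontinue therapy for serum creatinine greater than 2 times the age-appropriate ULN or for creatinine clearance less than 40 mL/min"). Its Section 8.6 asks for clearance to be calculated by Cockcroft-Gault "during treatment in all patients".

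Three other provisions bear on who is exposed. Inclusion 2 sets only a lower age limit ("Patients at least 18 years of age or older at the time of consent"), and no criterion sets a minimum weight. Inclusion 4 requires "Stable dosing with Jadenu or Exjade for >3 months prior to screening and receiving the maximal dose". Section 5.4 fixes the investigational dose: "Dosing will be at equivalent (mg for mg) doses of DST-0509 or Jadenu", with a 28/40 scaling for patients coming from Exjade.

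**The concern.** The protocol tightens the labels' creatinine limit from 2 to 1.5 × ULN but leaves out the clearance limit. One does not stand in for the other. For a given serum creatinine, clearance falls with age and low weight and is lower in women, so a slightly built or older patient can have a creatinine inside the 5c limit and a clearance below 40.

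Such a patient would take the comparator against a labelled contraindication and then take a new formulation of the same drug. Section 1.2 reports that DST-0509 was better absorbed than Exjade and Jadenu in fasted healthy volunteers. The labels carry a boxed warning for renal failure and describe the creatinine rise as dose-dependent. Safety is part of the primary objective, so a renal event in a patient who should not have entered would also be hard to interpret.

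**Working it through.** The plan states no figure to reproduce. The check is whether the 5c limit can be met with clearance below 40 mL/min.

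**Inputs**
- Creatinine limit: up to and including 1.5 × ULN is allowed (Section 4.2, 5c).
- Clearance limit: 40 mL/min (both labels, Section 4).
- Method: Cockcroft-Gault, as the labels specify.
- ULN: not given in the protocol. Assumed 1.1 mg/dL, with a range of 0.9 to 1.3.

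**Formula**

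CrCl = (140 − age) × weight × (0.85 if female) / (72 × SCr)

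**Clearance at the 5c limit**

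Worked example, woman of 40 y and 55 kg, ULN 1.1: SCr = 1.5 × 1.1 = 1.65 mg/dL, so CrCl = 100 × 55 × 0.85 / (72 × 1.65) = 4675 / 118.8 = 39.4 mL/min.

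| Profile | ULN 0.9 (SCr 1.35) | ULN 1.0 (SCr 1.50) | ULN 1.1 (SCr 1.65) | ULN 1.3 (SCr 1.95) |
|---|---|---|---|---|
| Woman 25 y, 45 kg | 45.3 | 40.7 | 37.0 | 31.3 |
| Woman 40 y, 45 kg | 39.4 | 35.4 | 32.2 | 27.2 |
| Woman 55 y, 45 kg | 33.4 | 30.1 | 27.4 | 23.2 |
| Woman 40 y, 55 kg | 48.1 | 43.3 | 39.4 | 33.3 |
| Woman 55 y, 55 kg | 40.9 | 36.8 | 33.4 | 28.3 |
| Man 55 y, 55 kg | 48.1 | 43.3 | 39.4 | 33.3 |
| Woman 25 y, 55 kg | 55.3 | 49.8 | 45.3 | 38.3 |
| Woman 40 y, 65 kg | 56.8 | 51.2 | 46.5 | 39.4 |
| Man 40 y, 55 kg | 56.6 | 50.9 | 46.3 | 39.2 |
| Woman 40 y, 75 kg | 65.6 | 59.0 | 53.7 | 45.4 |

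**Weight below which clearance is under 40 at the limit**

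Weight = 40 × 72 × SCr / [(140 − age) × (0.85 if female)]. With SCr 1.65 the numerator is 4752.

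| Age | Women | Men |
|---|---|---|
| 25 y | 48.6 kg | 41.3 kg |
| 40 y | 55.9 kg | 47.5 kg |
| 55 y | 65.8 kg | 55.9 kg |

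For a 40-year-old woman the cut-off runs from 3888 / 85 = 45.7 kg at ULN 0.9 to 5616 / 85 = 66.1 kg at ULN 1.3.

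**Creatinine at which clearance reaches 40 (women)**

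SCr = (140 − age) × weight × 0.85 / 2880, expressed against ULN 1.1:
- 40 y, 55 kg: 1.62 mg/dL, or 1.48 × ULN
- 55 y, 55 kg: 1.38 mg/dL, or 1.25 × ULN
- 40 y, 45 kg: 1.33 mg/dL, or 1.21 × ULN
- 55 y, 45 kg: 1.13 mg/dL, or 1.03 × ULN

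For some patients, then, the gap opens well below the 5c limit. At a creatinine of 1.1 mg/dL none of the tabulated profiles is under 40; the lowest is the woman of 55 y and 45 kg, at 3251.25 / 79.2 = 41.1.

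**The case against.** The strongest reply is that such a patient must already be treated against the label. Inclusion 4 requires more than three months of stable prescribed deferasirox at the maximal dose. Before reaching that point the labels ask the prescriber to measure clearance, halve the starting dose at 40 to 60 mL/min, monitor renal function at least monthly, cut the dose for a confirmed creatinine rise of 33% or more, and stop below 40. The comparator is the patient's own prescription, so the trial does not start it. Investigators hold both labels as appendices, Section 8.5.3 promises standard-of-care laboratory monitoring, and creatinine is measured on Days 1, 14, 28, 36, 49 and 63. Item 5d, exclusion 11 and the withdrawal criteria remove some further patients.

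This shrinks the group but does not empty it. None of these provisions is a clearance check at entry, and DST-0509 is a new exposure that the trial itself starts. During treatment, the only laboratory-triggered dosing rule in the protocol is the one for cytopenia. Withdrawal for renal toxicity rests on the investigator's judgement, with no threshold.

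A second reply is that the profiles depend on the assumed ULN. That is fair. Of the six profiles below 40 at ULN 1.1, three remain at 1.0 and two at 0.9. The two that remain, women of 45 kg aged 40 and 55, are below 40 throughout the range, so the direction does not depend on the assumption; the breadth does.

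**Conclusion.** The concern holds. As written, the entry criteria can admit a patient with clearance below 40 mL/min, whom both appended labels contraindicate, at the maximal dose of the comparator and with DST-0509 to follow. It takes a creatinine that is generally above normal but no more than 1.5 × ULN, together with low weight or older age. The size rests on an assumed ULN of 0.9 to 1.3 mg/dL and on Cockcroft-Gault. How many of the up to 36 patients would be affected cannot be worked out from the document, and the number is probably small. It is an omission in eligibility rather than in analysis, so no SAP could repair it. It is worth correcting because the possible harm is renal and avoidable.

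**What to change.** In Section 4.2 and in the synopsis, add an item to exclusion 5: creatinine clearance <40 mL/min (Cockcroft-Gault, from age, sex, body weight and serum creatinine at Visit 1). Keep the serum creatinine limit of 1.5 × ULN as it is.

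The cost is one line in each eligibility list and one calculated field on the CRF. Weight and chemistry are already obtained at Visit 1, so no sample or visit is added. A few otherwise eligible patients may be lost, all of them contraindicated by the appended labels.
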